5.2 Clinical Secondary Endpoint

- The severity of the ischemic stroke after surgery

- Number of patients occurred restroke at follow-up period
- Number of patients dependent (mRS > 2)or death at follow-up period
- Number of patients with improved neurological function at follow-up period
- Perfusion status of patients at follow-up period
- Number of patients with any side effects of remote ischemic preconditioning (RIPC) treatment.

6. Patient Selection Criteria

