Secondary endpoint	
 • The severity of the ischemic stroke after surgery • Number of patients occurred restroke at Follow-up Period • Number of patients dependent or death at follow-up period • Number of patients with improved neurological function at follow-up period • Perfusion status of patients at follow-up period • Number of patients with any side effects of remote ischemic preconditioning (RIPC) treatment.
Inclusion Criteria	
 • Patients who diagnosed with moyamoya disease • Adults 18 to 65 years of age • The onset symptoms manifested as ischemic symptoms (TIA or stroke) or atypical symptoms (headache, epilepsy or asymptomatic) • Able to receive the necessary imaging examination • Patients who pre-agreed to the study
Exclusion Criteria	
 • Prior cerebral hemorrhage history • Other brain or cerebrovascular disease • Previous history of revascularization surgery • Dependent (mRS > 2) • Receive other type of revascularization surgery • Peripheral blood vessel disease (especially subclavian arterial and upper limb artery stenosis or occlusion).

	
 • Patients who do not agree with the study
Sample Size	
Sample size and power were calculated based on previous studies and postoperative neurological complications, which were much better to indicate the efficacy of RIPC. We calculated the simple size and power with PASS, version 11 (NCSS, LLC, Kaysville, UT, USA). We expected ≈10% of subjects in the RIPC group and 20% of subjects in the other 2 groups would have new postoperative neurological complications. The intended target sample size was 328 subjects allowing 15% loss to follow-up and with 90% power and an α of 0.05 (2-sided) of significance.

Follow-up	
The face-to-face interview will be performed by study neurologists at discharge, at 6 months and at 12 months (or by telephone) after the recruitment of patients.

2. Study Rationale

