
4. Study Plan and Procedure

Study Design and Flow Chart

This study was a multi-center, prospective, randomized, controlled trial of

randomized (1:1) adult ischemic MMD patients undergoing indirect revascularization into two groups:

1. RIPC group

Remote limb ischemic preconditioning (RIPC) is consisted of five 5-min cycles of bilateral arm ischemia/reperfusion, it is induced by a sphygmomanometer placed on bilateral arm and inflated to 200 mmHg for 5-min followed by deflating the cuff for 5-min, patients in the RIPC group will do it twice a day for at least five days before EDAS.

2. sham RIPC group

Sham RIPC group is consisted of five 5-min cycles of bilateral arm ischemia/reperfusion, induced by a sphygmomanometer placed on bilateral arm and inflated to 60 mmHg for 5-min followed by deflating the cuff for 5-min, they will do it twice a day for at least five days before EDAS.

5. Study Endpoints

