5.1 Primary Endpoint

- All cerebrovascular events (ischemic stroke, cerebral hemorrhage, transient neurological dysfunction) within 30 days post-surgery
- All death or dependent (mRS > 2) within 30 days post-surgery

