13.2 Statistical Analyses

The results of the study were analyzed using IBM SPSS Statistics 23.0 (IBM Corp, Armonk, NY, USA) data analysis software. Charting was performed using GraphPad Prism 7.0a (GraphPad Software, La Jolla, CA, USA). Continuous variables obeying the normal distribution were expressed as mean \pm standard deviation, and two independent sample t-tests or paired t-tests were used for comparison between the two groups. Continuous variables with unknown distributions were expressed using median and interquartile range and compared between the two groups by Mann-Whitney U test or Wilcoxon rank sum test. The normality of the continuous variables

was tested using the Shapiro-Wilk W test. The categorical variables were expressed as frequency and percentage, and comparisons between the two groups were made using the Pearson chi-square test or the McNemar paired chi-square test. Correlation between the two variables was analyzed using Pearson, Kendall's tau-b or Spearman correlation coefficients according to the corresponding variable types. Prognostic information was analyzed by Kaplan-Meier survival analysis based on least squares method and compared between the two groups using log-rank test. All statistical tests were two-sided, and the results were considered statistically significant at $P < 0.05$.

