Symptomatic intracerebral hemorrhage	Any extravascular blood in the brain associated with clinical deterioration, as defined by an increase of 4 points or more in the score on the NIHSS, or that led to death and that was identified as the predominant cause of the neurologic deterioration. Intracerebral hemorrhage is defined as an acute extravasation of blood into the brain parenchyma. Criteria: evidence of hemorrhage in the brain parenchyma demonstrated by head imaging, surgery, or autopsy
Asymptomatic intracerebral hemorrhage	an acute extravasation of blood into the brain parenchyma without clinical deterioration. Criteria: evidence of hemorrhage in the brain parenchyma demonstrated by head imaging, surgery or autopsy
Other symptomatic intracranial hemorrhage	Any extravascular blood within the cranium associated with clinical deterioration, as defined by an increase of 4 points or more in the score on

	
the NIHSS, or that led to death and that was identified as the predominant cause of the neurologic deterioration. Other Intracranial Hemorrhage is defined as an acute extravasation of blood into the subarachnoid space, epidural space, or subdural space with associated symptoms. Criteria: evidence of hemorrhage in the subarachnoid space, epidural space, or subdural space demonstrated by head imaging, surgery, or autopsy

Other Asymptomatic intracranial hemorrhage
	
An acute extravasation of blood into the subarachnoid space, epidural space, or subdural space without associated symptoms. Criteria: evidence of hemorrhage in the subarachnoid space, epidural space, or subdural space demonstrated by head imaging, surgery, or autopsy

Ischemic vascular death
	
Death due to ischemic stroke, myocardial infarction, sudden cardiac death, arrhythmia, pulmonary embolism, bowel or limb infarction, or

	any death not readily attributable to a non- ischemic cause
Hemorrhagic Vascular death	Death due to intracranial or systemic hemorrhage
Dependent	Unable to look after own affairs without assistance, mRS score > 2

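### Stroke severity, as worded, exists only for patients who had a stroke, a group RIPC is meant to change, so the comparison is not randomised and its bias has no known direction

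*Combined protocol and SAP*

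**What the plan says.** The Synopsis and Section 5.2 both put "The severity of the ischemic stroke after surgery" first among the secondary endpoints. Neither names a scale, a time point or an analysis set. Neither gives a value for patients who have no stroke or who die.

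Section 13.2 assigns tests by type of variable and not by endpoint. A score of unknown distribution would be "compared between the two groups by Mann-Whitney U test or Wilcoxon rank sum test"; a normally distributed one would go to a t-test. No rule covers patients for whom the score does not exist.

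Ischemic stroke is itself a component of a primary endpoint: "All cerebrovascular events (ischemic stroke, cerebral hemorrhage, transient neurological dysfunction) within 30 days post-surgery" (Section 5.1). The sample size in Section 13.1 expects "10% of subjects in the RIPC group and 20% of subjects in the other 2 groups would have new postoperative neurological complications". Those rates cover all new neurological complications; the share that is ischemic stroke is not given.

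Two scales appear in the Appendix. The NIHSS occurs only in the definitions of symptomatic hemorrhage ("an increase of 4 points or more in the score on the NIHSS") and is not in the Schedule of Visits and Test. The mRS is scheduled at screening, discharge, later visits and event visits, but the plan does not link it to this endpoint.

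**The concern.** A severity score that starts at the occurrence of a stroke compares those sham patients who had a stroke with those RIPC patients who had one anyway. If RIPC works, these are different kinds of patient. The strokes it prevents leave the RIPC subset and take their severity with them, so the average among those remaining can move up, down or not at all, depending on which strokes were prevented.

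Two errors are possible. A real benefit that prevents mild and severe strokes in equal proportion leaves no trace in this endpoint. A real benefit that falls mainly on mild strokes can appear as a worsening of severity. Either could be reported under the first-listed secondary endpoint as a randomised finding, which it would not be.

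**Working it through.** **The plan's own figure.** The endpoint has no figure of its own. The trial size is stated as: "The intended target sample size was 328 subjects allowing 15% loss to follow-up and with 90% power". The usual two-proportion formula for 20% vs 10% gives n per arm = [1.960·√(2·0.15·0.85) + 1.282·√(0.2·0.8 + 0.1·0.9)]² / 0.10² = (0.990 + 0.641)²/0.01 ≈ 266. That is 532 in total, or 626 after dividing by 0.85, so 328 does not reproduce as a total (power at 328 is 72%). This is a separate matter. Here 328 is used only to obtain 328/2 = 164 per arm under 1:1 allocation.

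**Size of the stroke subset.** If every complication were an ischemic stroke, there would be 164 × 0.20 = 32.8 sham and 164 × 0.10 = 16.4 RIPC patients. After 15% loss (139.4 per arm) these become 27.9 and 13.9. They are upper bounds, because the rates also cover other complications.

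**Assumptions not in the documents.** Sham ischemic stroke rate 10% (range 5% to 20%). Half of sham strokes mild, scored evenly 1–4 (mean 2.5), and half severe, scored evenly 5–15 (mean 10). RIPC prevents a fraction *m* of mild and *s* of severe strokes and harms nobody.

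**Expected means at 10% sham strokes.** Sham has 16.4 strokes, 8.2 of each kind. The sham mean among strokes is (8.2·2.5 + 8.2·10)/16.4 = 6.25; over all 164 patients, with no stroke = 0, it is 102.5/164 = 0.625. For RIPC the total score is T = 8.2(1−m)·2.5 + 8.2(1−s)·10 and the number of strokes is K = 8.2(1−m) + 8.2(1−s). The stroke-only mean is T/K and the all-patient mean is T/164.

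| m | s | K | T | RIPC mean, strokes only (sham 6.25) | RIPC mean, all patients (sham 0.625) |
|---|---|---|---|---|---|
| 80% | 0 | 9.84 | 86.1 | 8.75 | 0.525 |
| 50% | 0 | 12.3 | 92.25 | 7.50 | 0.563 |
| 50% | 50% | 8.2 | 51.25 | 6.25 | 0.313 |
| 0 | 80% | 9.84 | 36.9 | 3.75 | 0.225 |

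The all-patient mean improves in every row. The stroke-only mean rises, stays the same or falls.

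**Simulated significance** (Mann-Whitney, two-sided 0.05, 164 per arm, 1,500 to 4,000 trials per setting; Monte Carlo standard error about 0.7 to 1.1 points at 27%).

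| Sham strokes | m | s | Stroke-only test | All randomised ranked |
|---|---|---|---|---|
| 10% | 50% | 50% | about 2% worse, about 2% better | better 41% |
| 20% | 50% | 50% | not tabulated | better 72% |
| 10% | 50% | 0 | worse 10% (estimate in the wrong direction in 77%) | not tabulated |
| 10% | 80% | 0 | worse 27%, median about 4 points higher | better 24%, worse under 0.3% |
| 5% | 80% | 0 | worse 11% | not tabulated |
| 20% (upper bound) | 80% | 0 | worse 52% | better 42–43%, worse 0.4% |
| 10% | 0 | 80% | worse 0.1%, better 26–27% | not tabulated |

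A separate run with 139 per arm and 20% sham strokes agrees in direction. Halving both kinds gave 2.4% significant each way, preventing half of mild strokes gave 16% false harm, and preventing all mild strokes gave 79%.

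**The case against.** The strongest reply is that the plan nowhere states a stroke-only test. That is correct: the restriction follows from the wording and from the absence of any value for stroke-free patients. The documented fault is an endpoint left undefined whose natural reading conditions on a post-randomisation event.

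A reader might infer that the endpoint would report harm from a beneficial treatment. The documents do not support this. Nothing in them says that RIPC prevents mainly mild strokes; with proportional prevention there is no bias towards harm, and with mainly severe strokes prevented the comparison points towards benefit. The 52% figure needs a 20% sham ischemic stroke rate, but 20% is the plan's rate for all complications, so 52% is an upper bound for that pattern. It is also tempting to fault the plan for not scheduling the NIHSS, but it never ties the NIHSS to ischemic stroke severity, and the scheduled mRS may have been intended.

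The primary endpoints count events, and death or dependency, in all patients. They limit the chance that a misleading severity result would go unnoticed, but they do not make the severity comparison valid.

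Ranking everyone is also not always more sensitive. If RIPC prevented no stroke but turned half of severe strokes into mild ones (20% strokes in both arms, 139 per arm), the stroke-only test found benefit in 36% of trials and the all-patient ranking in only 4%. That loss is real. The stroke-only test, however, is trustworthy only if treatment leaves stroke occurrence unchanged, which is contrary to the trial's premise.

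**Conclusion.** The point holds. As worded, the first-listed secondary endpoint compares a subset that treatment is meant to influence; randomisation does not protect the comparison, and the direction of its bias is unknown. At 10% sham strokes, half of them mild, a halving of all strokes is invisible (about 2% significant each way, against about 41% detected when all patients are ranked). Selective prevention of mild strokes gives false harm in 10% to 27% of trials. With 80% of mild strokes prevented, the range is 11% at 5% sham strokes to about 52% at the 20% upper bound.

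These sizes depend on the assumed stroke rate, severity mix and pattern of prevention, none of which the documents give. The structural fault does not depend on them. Apparent harm is a possibility under one pattern and not a prediction. The change should be made, but the primary comparison does not depend on it.

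**What to change.** Define severity within 30 days as one ordinal outcome in all randomised patients: no stroke best, then increasing severity, death worst. Compare arms by Mann-Whitney, which Section 13.2 already lists, and report the win probability (the chance that a random RIPC patient fares better than a random sham patient, ties counted half) with its confidence interval.

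- **Scale and time.** Name one scale and a fixed time. Either use the mRS, already scheduled at discharge and event visits, or use NIHSS change from baseline, with the NIHSS added at screening, discharge and the event visit. Change is needed because patients with a prior ischemic stroke are eligible. The schedule has no day-30 visit, so state which measurement counts for a stroke between discharge and day 30.
- **Hemorrhage.** State how hemorrhagic stroke is ranked, so that survivors of one do not fall in the best category.
- **Stroke patients.** Show severity among them by arm descriptively, without a test.

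The cost is SAP wording and, if the NIHSS is chosen, a short bedside score on the case report form. The ranking will have many ties and partly repeats stroke incidence from the primary endpoint. With the mRS it also overlaps the death-or-dependency primary endpoint. It will be weak if RIPC only makes strokes milder; the descriptive table is where that would show.

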6.1 Inclusion criteria

- Patients who diagnosed with moyamoya disease
- Adults 18 to 65 years of age
- The onset symptoms manifested as ischemic symptoms (TIA or stroke) or atypical symptoms (headache, epilepsy or asymptomatic)
- Able to receive the necessary imaging examination
- Patients who pre-agreed to the study

6.2 Exclusion Criteria

- Prior cerebral hemorrhage history
- Other brain or cerebrovascular disease
- Previous history of revascularization surgery
- Dependent (mRS > 2)
- Receive other type of revascularization surgery

- Peripheral blood vessel disease (especially subclavian arterial and upper limb artery stenosis or occlusion).
- Patients who do not agree with the study

7. Informed Consent

The principles of Informed Consent, according to FDA Regulations and ICH guidelines on GCP, will be followed. Investigator will submit a copy of the proposed consent form, together with the study protocol, to the central Institutional Review Board (IRB) at Beijing Tiantan Hospital for approval. Each eligible patient who wishes to participate in this study will be invited to give written informed consent. Before the consent is signed, a trained researcher will explain study purpose, description, duration, potential risks and anticipated benefits, cost and compensation, voluntary nature of participation, appropriate alternatives, treatment for study-related injury, whom to contact with questions or concerns or study-related injuries, maintenance of confidentiality of record, and funding source. Patients will be encouraged to consent for the blood drawing for biomarker testing only if they would be prepared to enroll in the trial.

8. Enrollment of Patients

All patients with moyamoya disease who visit the research center will be asked if they are involved in the study as long as they meet the inclusion criteria. This study is included in patients who have voluntarily participated in the study and signed

informed consent and did not meet the exclusion criteria.

9. Randomization of Patients

Patients was randomized by random number table

10. Image Data Evaluation

In this study, Suzuki staging was determined by DSA technique; subarachnoid hemorrhage, ischemic stroke (cerebral infarction), and cerebral hemorrhage were diagnosed using the Fourth National Conference on Cerebrovascular Diseases (1995).

In order to prevent errors in the research due to the interpretation technique, this study set up a decision-making committee to uniformly judge the imaging data of the patients enrolled. Two experienced neuroimaging physicians conducted mutual blind interpretation, and the results of the inconsistent report should be ranked third. The senior neuroimaging chief physician will conduct a trial and finally submit true and reliable imaging results for all cases. The interpreter does not participate in the study design and does not know the patient's clinical information.

11. Bio sample test

Blood samples were drawn from the cubital vein; the points of measurement included baseline, pre-EDAS, right 1 hour and 24 hours post-EDAS. The collected blood samples were sent for examination, and plasma neuron specific enolase (NSE) and human S protein 100B (S-100B) levels were examined in the test samples.

11. Schedule of Follow-up and Post-study Follow-up Period

All patients will be followed up until the primary endpoint or the end of the trial.

Complete endpoint information will be obtained with the best effort irrespective of patient study status, unless patients withdraw consent to participate the trial. The face-to-face interview will be performed by study neurologists at discharge, at 6 months and at 12 months (or by telephone) after the recruitment of patients.

Visits	Windows	Definition
Randomization	0 day	Study Day 0 day
At discharge	0 day	Based on the number of hospitalization days
At 6 months	14 days	Day 166-194
At 12 months	30 days	Day 330-390

12. Quality Assurance

Periodic monitoring and auditing will be performed at each site to ensure that data generated during the study reflect what is specified in the protocol, and data consistence by comparing data in the case report form (CRF) and data collected in source documents for (CRF vs. source documents). If patients who have events go to non-study sites for treatment, source documents will be photocopied for review. It should be guaranteed that the study investigators and relevant study personnel are available during the monitoring visits and possible audits.

13. Statistical Consideration

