13.1 Sample size estimates

This study was a cohort study of prospective, multicenter, hospital-based, continuous enrollment patients. It is planned to choose three hospitals in Beijing. The investigation and registration of the ending events are carried out through hospital follow-up examinations, investigations, registration and hotline reports, face-to-face or telephone follow-up, and monitoring information database supplementation.

Sample size and power were calculated based on previous studies and postoperative neurological complications, which were much better to indicate the efficacy of RIPC.

We calculated the simple size and power with PASS, version 11 (NCSS, LLC, Kaysville, UT, USA). We expected $\approx 10\%$ of subjects in the RIPC group and 20% of subjects in the other 2 groups would have new postoperative neurological complications. The intended target sample size was 328 subjects allowing 15% loss to follow-up and with 90% power and an α of 0.05 (2-sided) of significance.

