Protocol should be submitted to the Ethics Committee (IRB/IEC). It should also be informed of any event likely to affect the safety of patients or the continued conduct of the Clinical Trial, in particular any change in safety. All updates to the Investigator's Brochure will be sent to the Ethics Committee (IRB/IEC). If requested, a progress report will be sent to the Ethics Committee (IRB/IEC) annually and a summary of the Clinical Trial's outcome at the end of the Clinical Trial.

16. Safety Outcomes Assessment

The following adverse events were defined as safety outcomes: (1) elevation of plasma NSE and S-100B levels beyond normal limits after RIPC and sham RIPC procedure; (2) inability to tolerate RIPC or sham RIPC procedure that leads to the discontinuation from the study; (3) objective signs of tissue or neurovascular injury resulting from RIPC and sham RIPC procedure. An inspection that was done by staffs blinded to the study protocol included palpation of distal radial pulses, visual inspection for local edema, erythema and skin lesions, and palpation for tenderness. These safety outcomes were evaluated by observers blinded to the treatment assignment, and any suspicious adverse event associated with RIPC or sham RIPC procedure was reported to the investigators.

APPENDIXS

Study Flow Chart

Schedule of Visits and Test

	Visit 1	Visit 2	Visit 3	Visit 4	Event visit
Assessments	Screening/Randomize	At discharge	At 1 year ± 1 month	Every 12 months ±1 month	
Informed Consent	✓				
Eligibility criteria	✓				
Patient Randomization	✓				
Relevant medical history	✓				
Demographics	✓				
MRI before Surgery	✓				
CTP before Surgery	✓				
DSA before Surgery					
Vital signs	✓				✓
Modified Rankin Score	✓	✓	✓	✓	✓
MRI after surgery		✓	✓	✓	
CTP after surgery		✓	✓	✓	✓
DSA after surgery		✓	✓		✓
Current Medications	✓	✓	✓	✓	✓
Endpoints		✓	✓	✓	✓

modified Rankin Scale

The modified Rankin Scale (mRS) is a scale commonly used for measuring the degree of disability or dependence in the daily activities of individuals who have suffered a stroke, and it has become the most widely used clinical outcome measure for stroke clinical trials.

Description	Score (select one)
No symptoms at all	0 
No significant disability despite symptoms; able to carry out all usual duties and activities	1 

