Slight disability; unable to carry out all previous activities, but able to look after own affairs without assistance	2 
Moderate disability; requiring some help, but able to walk without assistance	3 
Moderately severe disability; unable to walk without assistance and unable to attend to own bodily needs without assistance	4 
Severe disability; bedridden, incontinent and requiring constant nursing care and attention	5 

Dead

6

Definition of End Points

Stroke
	
Sudden symptoms and signs of focal disturbance of cerebral function associated with cerebral circulation disorders.

Ischemic stroke
	
An acute focal infarction of the brain or retina.
 
Criteria: (1) acute onset of a new focal neurological deficit with clinical or imaging evidence of infarction lasting more than 24 hours and not attributable to a non-ischemic etiology (not associated with brain infection, trauma, tumor, seizure, severe metabolic disease, or degenerative neurological disease); or (2) acute onset of a new focal neurological deficit and not attributable to a non-ischemic etiology lasting less than 24 hours, but accompanied by neuroimaging evidence of new brain infarction; or, (3) rapid worsening of an existing focal neurological deficit lasting more than 24 hours and not attributable to a non-ischemic etiology, and accompanied by new ischemic changes on brain MRI or CT, and clearly

	distinct from the index ischemic event.
Hemorrhagic stroke	An acute extravasation of blood into the brain parenchyma or subarachnoid space with associated neurological symptoms.
TIA	A neurological deficit of sudden onset, resolving completely, attributed to focal brain or retinal ischemia without evidence of associated acute focal infarction of the brain. Criteria: rapid onset of a focal neurological deficit that is without evidence of acute focal infarction of the brain, and is not attributable to a non-ischemic etiology (brain infection, trauma, tumor, seizure, severe metabolic disease, or degenerative neurological disease)
Transient neurological deficits (TNDs)	Either any reversible neurological deficit observed objectively (e.g., hemiparesis, dysarthria) or any reversible neurological deficit recognized and reported subjectively (e.g., facial palsy), without evidence of intracranial hemorrhage and cerebral

	infarction on imaging studies.

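### Both primary endpoints close 30 days after surgery, but no contact is planned near postoperative day 30

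*Combined protocol and SAP*

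**What the plan says.** Section 5.1 sets two primary endpoints, both timed from surgery: "All cerebrovascular events (ischemic stroke, cerebral hemorrhage, transient neurological dysfunction) within 30 days post-surgery" and "All death or dependent (mRS > 2) within 30 days post-surgery". The synopsis gives the same windows.

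Two schedules govern when patients are seen.

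- **Section 11 (Schedule of Follow-up and Post-study Follow-up Period):** "The face-to-face interview will be performed by study neurologists at discharge, at 6 months and at 12 months", with telephone as an alternative, counted from recruitment. Its table makes randomisation day 0, ties the discharge visit to length of stay rather than to a fixed day, and places the later visits at Day 166-194 and Day 330-390.
- **Appendix, Schedule of Visits and Test:** after discharge the next column is "At 1 year ± 1 month", then a visit every 12 months, plus an unscheduled Event visit. There is no 6-month visit. mRS is ticked at screening, discharge, the later visits and the Event visit.

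Other routes to endpoint information are named without dates. Section 11 promises: "Complete endpoint information will be obtained with the best effort irrespective of patient study status". Section 13.1 lists hospital examinations, hotline reports, "face-to-face or telephone follow-up, and monitoring information database supplementation". Section 12 provides for copying source documents when a patient with an event is treated elsewhere.

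The Appendix definition of transient neurological deficits includes "any reversible neurological deficit recognized and reported subjectively (e.g., facial palsy") and requires imaging that shows neither haemorrhage nor infarction. Section 13.2 compares categorical outcomes by chi-square test and has no rule for a patient about whom nothing is known between discharge and day 30.

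**The concern.** The primary outcome has a fixed window, but direct observation ends at discharge, which comes on a different day for each patient. After that, an event enters the primary count only if someone reports it or a patient recalls it months later.

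This matters little for events that leave a dated record: stroke, haemorrhage and death. It matters for two components that may leave none.

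1. **mRS > 2 arising after discharge.** A discharge score above 2 inside the window can count as an endpoint. A discharge score of 0-2 does not show that the patient stayed independent to day 30, and a score taken at 6 or 12 months does not show it either.
2. **Transient deficits.** They resolve, may be known only from the patient's account, and by definition leave no infarct or haemorrhage on imaging. A later scan cannot reveal one that was missed.

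Three hospitals are planned. Without a common contact, capture of these components would depend on who reports and on how each hospital follows its patients. With no rule for missing information, patients not heard from may be counted as event-free by default.

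**Working it through.** **Inputs from the documents**

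- Endpoint window: 30 days from surgery (section 5.1).
- Conditioning: "twice a day for at least five days before EDAS" (section 4). If it starts no earlier than randomisation on day 0, surgery falls on study day S with S ≥ 5. No upper limit on S is given.
- First planned contact after discharge: Day 166-194 (section 11), or one year ± one month (Appendix).

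**Assumptions, not in the documents**

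- S = 14 and S = 30, to show later surgery.
- The Appendix year is day 365 ± 30 from recruitment, that is day 335-395.
- Postoperative stays of L = 5, 7, 10, 14 and 21 days.

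**Step 1. Reproduce the plan's visit windows.** 180 ± 14 gives 166-194, and 360 ± 30 gives 330-390. Both agree with the section 11 table.

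**Step 2. Time from the close of the window to the next planned contact.** The window closes on study day S + 30. The gap is the visit day minus (S + 30).

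| Surgery on study day S | Window closes | Gap to section 11 6-month visit | Gap to Appendix 1-year visit |
|---|---|---|---|
| 5 | day 35 | 166 − 35 = 131 to 194 − 35 = 159 | 335 − 35 = 300 to 395 − 35 = 360 |
| 14 | day 44 | 122 to 150 | 291 to 351 |
| 30 | day 60 | 106 to 134 | 275 to 335 |

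The gap is more than 100 days in every row, under either schedule.

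**Step 3. Part of the window with no planned contact.** For a stay of L days after surgery this is 30 − L.

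| Postoperative stay L | Days without planned contact | Share of the 30 days |
|---|---|---|
| 5 | 25 | 83% |
| 7 | 23 | 77% |
| 10 | 20 | 67% |
| 14 | 16 | 53% |
| 21 | 9 | 30% |

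These are shares of calendar days, not of events. Complications may cluster before discharge, so the share of events at risk of being missed could be much smaller.

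**Step 4. Can the other routes fill the gap?** An Event visit requires that someone already knows of an event. The hotline, telephone, database and hospital follow-up routes have no stated date or frequency. None gives every patient an mRS or an event check covering the days from discharge to day 30.

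**The case against.** The strongest reply is that the plan does not abandon patients after discharge. Section 11 opens with a general commitment to follow everyone to the primary endpoint or the end of the trial, and section 13.1 includes hospital examinations and telephone follow-up, which are not purely passive. Patients already dependent at entry are excluded, so reaching mRS > 2 takes real deterioration. If a stroke or haemorrhage causes it, an Event visit should record the mRS. The second endpoint is defined over the 30 days, so it does not clearly require a score on day 30 itself. Both arms use the same follow-up routes in a sham-controlled design, and nothing suggests that capture would differ between them. The study flow chart could not be read in the text available for this review and might show a further contact.

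Much of this stands. It narrows the problem to functional decline that triggers no Event visit and to transient deficits, and it means that no bias between arms has been shown. It does not supply a dated contact: the general commitments name no time point, and neither readable schedule has one.

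A further fair point is that a call at day 30 cannot provide imaging for a deficit that has already resolved, and it still relies on recall since discharge. That limits the benefit of the call. Recall over at most 30 days is nevertheless a better basis than recall over several months.

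**Conclusion.** The concern holds. In both readable schedules, a patient discharged before postoperative day 30 with no reported event has no planned check of either primary endpoint until at least 106 days after the window closes (section 11), or at least 275 days (Appendix), for surgery between study day 5 and day 30. The rest of the window would be classified from discharge status, from unscheduled reports or from late recall, so the primary event count would be incomplete and not standardised across hospitals.

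The number of events lost is not known. The documents give neither length of stay nor the share of events after discharge, so no effect on event rates or power is claimed. The day counts rest on the assumed surgery days and, for the Appendix, on a 365-day year. The absence of a day-30 contact rests on no assumption. This is an inexpensive improvement to make, not a reason to reject the design.

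**What to change.** - **Add one contact anchored to surgery**, for example at postoperative day 30 to 35 so that the full window has elapsed, by telephone where needed. Record mRS, vital status and a scripted, dated check for ischaemic stroke, haemorrhage and transient deficits since discharge.
- **Name the data sources for both primary endpoints**: in-hospital records, the discharge visit, Event visits and this contact.
- **State two rules in advance**: how a transient deficit reported without imaging is classified, and how a patient with no information between discharge and day 30 is handled in the analysis.
- **Separately, reconcile section 11 with the Appendix** on whether a 6-month visit exists, so that the follow-up endpoints have one fixed time point.

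The cost is a short protocol amendment and one extra scripted contact per patient, up to 328 at the target sample size. Study neurologists already carry out the follow-up interviews and telephone contact is already accepted. The documents do not state staff capacity, so the three hospitals would need to confirm it.
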